9.6 Secondary Endpoint(s)

9.6.1 Secondary Safety Endpoint(s)

The following adjudicated events will be evaluated as secondary safety endpoints during the twelve-month follow-up period:

1. Acute myocarditis possibly attributable to CAP-1002 or placebo, diagnosed with consideration of clinical context, with or without a clinically indicated endomyocardial biopsy. In order to be considered related to CAP-1002 or placebo, humoral or cellular immune reaction specific to CAP-1002 must also be documented for subjects treated with CAP-1002, or a temporal relationship with IP administration must exist for subjects administered placebo.
2. Death due to ventricular tachycardia or ventricular fibrillation defined as occurring with prior ECG documentation of these arrhythmias during ambulatory ECG monitoring in an outpatient setting or during routine ECG monitoring while hospitalized.
3. Sudden unexpected death defined as occurring within one hour of symptom onset, or unwitnessed death in a person previously observed to be well within the preceding 24 hours without an identified cause.
4. Major adverse cardiac event (MACE), defined as the composite incidence of death, non-fatal recurrent MI, hospitalization for heart failure, emergency room treatment for heart failure (NT-proBNP >450 pg/mL or BNP>100 pg/ml, with treatment including intravenous diuretic administration), left ventricular assist device (LVAD) placement or heart transplant. Peri-infusion MI will be defined as presence of troponin or CK-MB levels > 5 times the upper reference limit during the 24 hours following infusion. These elevations must be accompanied by symptoms of ischemia > 20 minutes in duration and ECG changes indicative of new ischemia (new ST-T changes or new left bundle branch block), development of pathological Q waves on the ECG, imaging evidence of new loss of viable myocardium, or

new regional wall motion abnormality.

5. New cardiac tumor formation on MRI imaging.
6. Any hospitalization due to a cardiovascular cause or related to CAP-1002 or placebo infusion.
7. Any inter-current cardiovascular illness or one related to CAP-1002 or placebo infusion, which prolongs hospitalization. Evidence of myocardial injury will be assessed by a rule out MI cardiac enzyme protocol performed following administration of CAP-1002 or placebo. Troponin and CK-MB will be obtained approximately every 8 hours for the first 24 hours after infusion.

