### 2.3 Study Endpoints and Hypotheses

#### 2.3.1 Primary Safety Endpoint

The primary safety endpoint is whether or not any of the following adjudicated (see [Section 12](#)) events occur during the one month post intracoronary infusion:

1. Acute myocarditis possibly attributable to the investigational product (IP), diagnosed with consideration of clinical context, with or without a clinically indicated endomyocardial biopsy. In order to be considered related to the IP, humoral or cellular immune reaction specific to CAP-1002 must also be documented for subjects treated with CAP-1002, or a temporal relationship with IP administration must exist for subjects administered placebo. See [Section 12](#) for further information related to blinded adjudication by the Clinical Events Committee (CEC).
2. Death due to ventricular tachycardia or ventricular fibrillation defined as occurring with electrocardiogram (ECG) documentation of these arrhythmias during ambulatory ECG monitoring in an outpatient setting or during routine ECG monitoring while hospitalized.
3. Sudden unexpected death defined as occurring within one hour of symptom onset, or unwitnessed death in a person previously observed to be well within the preceding 24 hours without an identified cause.
4. Major adverse cardiac event (MACE), defined as the composite incidence of death, nonfatal recurrent MI, hospitalization with primary discharge diagnosis of heart failure, emergency room treatment for heart failure [ N-terminal pro-hormone brain natriuretic peptide (NT-proBNP)  $> 450$  pg/mL or brain natriuretic peptide (BNP)  $> 100$  pg/ml, with treatment including intravenous diuretic administration], LV assist device (LVAD) placement or heart transplant. Peri-infusion MI will be defined as presence of troponin or creatine phosphokinase MB isoenzyme (CK-MB) levels  $> 5$  times the upper reference limit during the 24 hours following infusion. These elevations must be accompanied by symptoms of ischemia  $> 20$  minutes in duration and ECG changes indicative of new ischemia (new ST-T changes or new left bundle branch block), development of pathological Q waves on the ECG, imaging evidence of new loss of viable myocardium, or new regional wall motion abnormality.

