### **2.3.3 Secondary Safety Endpoints**

The following adjudicated (see [Section 12](#)) events will be evaluated as secondary safety endpoints over the twelve-month follow-up period:

1. Acute myocarditis possibly attributable to the IP, diagnosed with consideration of clinical

context, with or without a clinically indicated endomyocardial biopsy. In order to be considered related to the IP, humoral or cellular immune reaction specific to CAP-1002 must also be documented for subjects treated with CAP-1002, or a temporal relationship with IP administration must exist for subjects administered placebo. See [Section 12](#) for further information related to blinded adjudication by the CEC.

2. Death due to ventricular tachycardia or ventricular fibrillation defined as occurring with prior ECG documentation of these arrhythmias during ambulatory ECG monitoring in an outpatient setting or during routine ECG monitoring while hospitalized.
3. Sudden unexpected death defined as occurring within one hour of symptom onset, or un-witnessed death in a person previously observed to be well within the preceding 24 hours without an identified cause.
4. MACE, as defined above.
5. New cardiac tumor formation on magnetic resonance imaging (MRI).
6. Any hospitalization due to a cardiovascular (CV) cause or related to IP infusion.
7. Any inter-current CV illness, or one related to IP infusion, which prolongs hospitalization. Evidence of myocardial injury will be assessed by a rule out MI cardiac enzyme protocol performed following IP administration. Troponin and CK-MB will be obtained approximately every 8 hours for the first 24 hours after infusion.
8. New TIMI flow  $\leq 1$  following IP infusion.
9. Development of, or an increase in the frequency of, ventricular tachycardia with a duration of 30 beats or longer ascertained by periodic, protocol-mandated 24 hour ambulatory ECG monitoring.

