## 10.2 Secondary Safety Endpoints

The secondary safety endpoints include clinical events, as described in [Section 2.3.3](#). The secondary safety endpoint listing will include indicators for each event, study day of the event, and total days of follow-up. Each endpoint will be summarized as frequency of subjects who experienced the endpoint and event rate per 100 subject-years. The summary table of the clinical event endpoints will also include a p-value for the comparison of event rate between treatment groups based on negative binomial regression with an offset for days of follow-up (log transformed). If the dispersion parameter is not significantly different from zero, Poisson regression will be used instead. Since the clinical event endpoints account for differential length of follow-up, handling of missing data is not applicable.

For the analysis of the secondary safety endpoint of development of increased HLA antibody levels to HLA antigens specific to the CAP-1002 CDC donor, incidence of increased HLA antibody levels, specific to the donor, will be summarized and analyzed; for placebo subjects, a random donor will be selected from those that were matched to the subject during screening. Elevated levels of DSA will also be summarized and analyzed by time point for all nominal time points at which samples were collected for DSA testing. Analyses will be performed using both 5000 and 1000 MFI as the threshold for defining increased HLA antibodies.

One secondary safety endpoint, new TIMI flow  $\leq 1$ , would only occur intra-procedurally and will be analyzed using a chi square or Fisher's exact test instead of negative binomial or Poisson regression.

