## 12. CLINICAL EVENTS COMMITTEE

In order to apply some level of consistency and standardization, the following will be adjudicated by a CEC:

- Primary and secondary safety endpoints with the following exceptions:
  - The CEC will refer any potential case of acute myocarditis to the DSMB in order to make a final ruling on whether the clinical event meets the protocol-defined definition of acute myocarditis. The DSMB will be unblinded to humoral and cellular immunology data.
  - Development of increased anti-HLA antibody levels with development of sensitization to HLA antigens specific to the CAP-1002 CDC donor. The DSMB clinical immunologist will be unblinded to all available DSA data during the conduct of the trial.
- AEs occurring within 24 hours of IP administration.
- AEs judged by the investigator as possibly, probably or definitely related to the IP or IP administration procedure, reported at any time.
- Treatment-emergent SAEs.

The CEC will follow consensus definitions of CV endpoint events. In the case where the protocol explicitly provides an endpoint definition, the CEC will adjudicate the clinical event according to the protocol definition and then, separately, according to the consensus definition. In the case where the protocol provides only a partial definition (e.g., “emergency room treatment for heart failure”) or is silent on the definition of the endpoint, the consensus definition, if it exists, will be used.

For safety endpoints, a hierarchy will be applied for a clinical event that could be adjudicated in multiple categories so that a clinical event is counted only once. The hierarchy, from highest severity to lowest, will be death > heart failure hospitalization > CV-related hospitalization. Any adjudicated event not otherwise named in the consensus definitions will be MedDRA-coded.

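### Read literally, the SAP's count-once hierarchy removes heart-failure admissions from a secondary safety endpoint defined as any cardiovascular hospitalisation

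*SAP*

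**What the plan says.** **Endpoint definition.** The sixth secondary safety endpoint in SAP 2.3.3 is "Any hospitalization due to a cardiovascular (CV) cause or related to IP infusion". Protocol 9.6.1 has essentially the same definition: "Any hospitalization due to a cardiovascular cause or related to CAP-1002 or placebo infusion". Neither excludes heart-failure admissions or admissions that end in death.

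**Counting rule.** SAP 12 applies a ranking to the safety endpoints when one event fits more than one category, "so that a clinical event is counted only once". In order, the ranks are "death > heart failure hospitalization > CV-related hospitalization".

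**Where the higher ranks sit.** Death and "hospitalization with primary discharge diagnosis of heart failure" are components of MACE (SAP 2.3.1), which is the fourth item in both the primary and the secondary safety lists. CV-related hospitalisation is not a MACE component.

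**Analysis.** SAP 10.2 treats the secondary safety endpoints one by one: "Each endpoint will be summarized as frequency of subjects who experienced the endpoint and event rate per 100 subject-years". For the clinical event endpoints it adds a p-value from negative binomial regression, or Poisson regression if there is no overdispersion.

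**Declared changes.** The protocol's endpoint lists contain no hierarchy. SAP 14 reports no deviations from the protocol's statistical methods.

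**The concern.** A heart-failure admission fits both of the lower ranks: it is a heart-failure hospitalisation and also a hospitalisation with a cardiovascular cause. If it is counted once, at the higher rank, it is not counted as a CV-related hospitalisation. The only listed endpoint that matches the bottom rank is endpoint 6. The rule therefore turns an endpoint defined as *any* cardiovascular admission into one that leaves out heart failure.

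This matters because the trial enrols patients with a previous MI and an LVEF of 0.45 or less, for whom heart failure is an obvious reason for admission. A subject whose only cardiovascular admission was for heart failure would be tabulated as having had none. The distortion can also depend on treatment: an effect of CAP-1002 on heart-failure admissions, in either direction, would not show in the endpoint 6 row. SAP 13.1 sends the secondary safety endpoints to the DSMB, so interim reviews would carry the same row.

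**Working it through.** The plan states no rate, power or sample size for this endpoint, so there is no figure of its own to reproduce. The check is a reading of the text, followed by an illustration.

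**Step 1: the text**

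| Event | Meets the endpoint 6 definition? | Rank under SAP 12 | Counted in endpoint 6 under the hierarchy? |
|---|---|---|---|
| CV admission, not for heart failure, subject survives | Yes | CV-related hospitalisation | Yes |
| Heart-failure admission, subject survives | Yes | Heart-failure hospitalisation | No |
| CV admission ending in death | Yes | Death, if admission and death are one clinical event | No, on that assumption |

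The second row needs only that heart failure is a cardiovascular cause. The third row needs more, because the SAP does not say whether an admission and a death that follows it are one event or two. The illustration below therefore uses heart-failure admissions only.

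The primary safety endpoint does not change. It records whether a subject had any qualifying event. Death and heart-failure hospitalisation both sit inside its MACE component, and CV-related hospitalisation is not part of it.

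**Step 2: events lost (illustration)**

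Inputs from the documents: about 69 CAP-1002 and 34 placebo subjects in the Primary Randomized Cohort (protocol synopsis, Study Population), and 12 months of follow-up, giving 69 and 34 subject-years if all are followed in full. Assumed inputs: a CV admission rate R of 20 to 40 per 100 subject-years, equal in both arms, and a heart-failure share s of 20% to 60% of those admissions.

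Events kept = subject-years × R × (1 − s).

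| | Placebo | CAP-1002 |
|---|---|---|
| All, R = 20 per 100 | 34 × 0.20 = 6.8 | 69 × 0.20 = 13.8 |
| All, R = 40 per 100 | 34 × 0.40 = 13.6 | 69 × 0.40 = 27.6 |
| Fewest kept (R = 20 per 100, s = 60%) | 6.8 × 0.4 = 2.7 | 13.8 × 0.4 = 5.5 |
| Most kept (R = 40 per 100, s = 20%) | 13.6 × 0.8 = 10.9 | 27.6 × 0.8 = 22.1 |

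The proportional loss is s itself, 20% to 60%, whatever R is.

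**Step 3: effect on the comparison (same assumed range of s)**

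Let m be the rate ratio for heart-failure admissions, with other admissions unchanged. The rate ratio for endpoint 6 as defined is s × m + (1 − s). With heart failure removed it is 1.00.

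- m = 2: 0.2 × 2 + 0.8 = 1.2, up to 0.6 × 2 + 0.4 = 1.6. The reduced row shows 1.00, so the excess is masked.
- m = 0.5: 0.2 × 0.5 + 0.8 = 0.9, down to 0.6 × 0.5 + 0.4 = 0.7. The reduced row shows 1.00, so a benefit is masked too.
- A quarter of non-heart-failure admissions become heart-failure admissions, total unchanged: the ratio for endpoint 6 as defined is 1.00, and the reduced row shows 1 − 0.25 = 0.75. Over the same range the ratio for the heart-failure component of MACE is (0.2 + 0.25 × 0.8)/0.2 = 2.0, down to (0.6 + 0.25 × 0.4)/0.6 = 1.17. The counter-signal is present, but in another row.

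**Step 4: subjects rather than events**

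Suppose 20% of subjects have a CV admission, 40% of those have a heart-failure admission, and a fraction q of the latter also have a non-heart-failure one. The proportion shown is 20% × (1 − 0.40 × (1 − q)). With q = 0 this is 12%; with q = 0.5 it is 16%; with q = 1 it is 20%. Twelve per cent is therefore the floor under these assumptions.

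**The case against.** The best defence is that the hierarchy gives each event one label and does not define the endpoints. It sits in the adjudication section. It does not name the infusion-related limb of endpoint 6, and it does not rank other overlaps in the list, such as the death endpoints with MACE, or endpoint 7 with endpoint 6. As an exclusion rule across endpoints it would be incomplete. The preceding paragraph of SAP 12 has the committee adjudicate to the protocol's definition wherever the protocol gives one explicitly, and a heart-failure admission meets the protocol's endpoint 6. SAP 10.2 plans an indicator for each event and never mentions the hierarchy. The protocol (7.4) also refers to a separate adjudication manual, not available here, which may settle the matter.

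That reading is possible, but neither document states it. SAP 12 applies the rule to safety endpoints without limiting it to a pooled tally or a label, so a programmer following the text could properly drop the admissions.

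The defence is right about consequences. The admissions and deaths remain in MACE within the same secondary analysis, admissions that meet the seriousness criteria appear in the treatment-emergent SAE table, deaths have their own table, and the DSMB receives SAEs as well as endpoints. The protocol synopsis treats secondary safety analyses as descriptive, and no decision rule uses endpoint 6.

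A reader might infer three stronger things that the documents do not support:

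- *That fatal admissions certainly leave endpoint 6.* This depends on an undefined unit of counting.
- *That a shift from heart-failure admission to death would lower endpoint 6.* Heart-failure admissions are already outside the row under this reading, so such a shift leaves it unchanged.
- *That the safety report as a whole hides these events.* Only one row is affected.

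**Conclusion.** The concern holds in a limited form. SAP 12, taken at its word, conflicts with the definition of endpoint 6 in both documents. It would make that endpoint's frequency, rate and p-value refer to cardiovascular admissions other than heart failure. Admissions ending in death would go too, but only if admission and death are treated as one clinical event.

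The size is unknown, because the documents give no admission rates. On an assumed heart-failure share of 20% to 60%, the row loses that share of its events, and fewer subjects wherever some have both kinds of admission. Within the row, an excess of heart-failure admissions is masked, and a shift from other admissions to heart failure looks like a reduction. MACE and the SAE and death tables still carry the events, and the primary safety composite is untouched. This is worth correcting before analysis, as a definitional conflict in one secondary safety endpoint. It does not threaten the trial's main safety conclusion.

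**What to change.** State in SAP 12 that each listed safety endpoint counts every event meeting its own definition, so that one admission may contribute to both MACE and endpoint 6. State also that the hierarchy is used only for a separate, mutually exclusive worst-event summary, and define whether an admission and a death during it are one event or two for that summary.

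The cost is a short SAP clarification and one extra summary, with no new data. The small downside is that the endpoint rows overlap and cannot be summed, which a table footnote can say. If the narrower endpoint is really intended, rename it to say that heart-failure (and, if so decided, fatal) admissions are excluded, and list the change in SAP 14.

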## 13. SEQUENCE OF PLANNED ANALYSES

### 13.1 Interim Safety Reviews

An independent DSMB appointed by the Sponsor, separate from the National Institutes of Health (NIH) DSMB used for ALLSTAR Phase 1, will oversee ALLSTAR Phase 2. Interim safety reviews will be conducted at intervals not to exceed 6 months apart. The DSMB will evaluate unblinded safety data in the form of TFLs and/or narratives.

Data on the following will be provided to the DSMB for review:

- Subject disposition
- Demographic and other baseline characteristics
- IP administration details
- Primary and secondary safety endpoints
- TEAEs and SAEs
- Safety laboratory evaluations
- Concomitant cardiac medications

### 13.2 Interim Analyses

#### 13.2.1 DSMB Safety

Periodic safety reviews of the safety population will be overseen by the DSMB. Analyses of the primary safety endpoint will include tests of the one-sided hypothesis that the difference in rates between the CAP-1002 and placebo treatment groups is no greater than 20% (see [Section 2.3.2](#)). In addition, the proportion of subjects experiencing serious procedure-related outcomes (SPROs) will be monitored. A series of charts are provided in the protocol to assist with this oversight. These “stopping” guidelines will serve as a trigger for consultation with the DSMB for additional review and do not mandate automatic closure of study enrollment. Stopping will be at the discretion of the Sponsor, after consideration of DSMB recommendations.

#### 13.2.2 Administrative Safety and Efficacy

An administrative interim safety and efficacy analyses will be performed when all subjects in the primary mITT population have completed the Month 6 visit or have discontinued from the study. An additional administrative interim analyses may be conducted on an as-needed basis. Results from interim efficacy analyses will be used for business planning activities and will have no effect on the conduct of Phase 2. As such, there will be no statistical penalty applied to the final efficacy analysis as a result of interim efficacy analyses.

### 13.3 Final Analysis

The final analysis will occur when all subjects have reached EOS (completed the Month 12 visit or discontinued), all clinical data have been entered into the data capture system, AE and concomitant medication data have been coded, quality control checks have been completed, all

data queries have been resolved, protocol violations/ deviations have been identified, and the database has been locked.

#### **14. DEVIATIONS FROM STATISTICAL METHODS IN THE PROTOCOL**

None.

## APPENDIX A: SCHEDULE OF EVENTS

Study Procedure	Screening	Pre-Infusion	Infusion	2 Weeks	1 Month	2 Months (Phase 1 Only)	3 Months	6 Months	12 Months /ET	24, 36, 48, 60 Months Follow-Up
Study Day	Day -28	Day 0	Day 0	Day 14 ±3d	Day 30 ±3d	Day 60 ±6d	Day 90 ±6d	Day 180 ±6d	Day 360 ±6d or ET	Annual ±2w
Relative Timing	Post-MI	≤28d Screen	≤28d Screen	Post Infusion	Post Infusion	Post Infusion	Post Infusion	Post Infusion	Post Infusion	Post Infusion
Informed Consent	X 									
Medical History	X 	X								
Limited Physical Examination	X 								X	
History and Cardiac Physical	X 	X	X	X	X	X	X	X	X	
Medication Review	X 	X	X	X	X	X	X	X	X	
Adverse Events Assessment	X 	X	X	X	X	X	X	X	X	
Major Adverse Cardiac Events			X	X	X	X	X	X	X	X
Vital Signs	X 	X	X	X	X	X	X	X	X	
12-Lead ECG	X 	X	X	X	X	X	X	X	X	
Hematology, Chemistry, & Urinalysis	X 	X	X	X	X	X	X	X	X	
PTT / INR		X 								
Serum NT-proBNP	X 	X	X	X	X	X	X	X	X	
Serum for Biomarkers	X 			X 	X 	X 	X 	X 	X 	X
Serum β-HCG	X 									
HIV & Hepatitis Screens; Hemoglobin A1c (HbA1c)	X 									
Donor Specific Antibody (DSA)	X 			X 	X 	X 	X 	X 	X 	X
HLA Typing	X 									
ELISpot	X 				X 					
Cardiac MRI	X 							X	X	
Chest, Abdomen, and Pelvis CT	X 									
24 Hour Ambulatory ECG	X 		X 		X	X		X	X	
Serum troponin & CK-MB		X 	X 	X	X					
Echocardiography	X 				X					
NYHA Functional Class	X 				X	X	X	X	X	
Six Minute Walk Test	X 							X	X	
Patient Questionnaires	X 							X 	X 	
Intracoronary Infusion; 24 Hr Hospitalization w/ Continuous			X							

 Permitted within 28 days immediately following index MI: signing ICF, review of medical history, review of concomitant medications, and collection of laboratory samples required for assessment of study eligibility criteria (e.g., eGFR, HbA1c, hepatitis serology, HIV serology, LFTs, hematocrit, WBC, serum β-HCG and platelet count).

 Must be performed >28 days post-MI and ≤28 days of infusion. Repeat hematology, chemistry & urinalysis if initial testing to assess eligibility falls outside of this window. For post infusion, urinalysis only.

 Every 8 hours from time of infusion until discharge.

 On day of discharge.

 Urinalysis only.

 For subjects on anticoagulation therapy only.

 Only if additional consent is obtained; collection for shipment to central laboratory.

 Non-postmenopausal females only.

 Troponin and CK-MB pre-infusion and approximately every 8 hours post infusion.

 Collection of blood for testing at central laboratory.

 Starting immediately prior to discharge for 24 hours.

 MLHFQ, SF-36, WPAI:SHP and Patient Global Assessment.

